# 13.4.3 Efficacy Analyses

All efficacy measures will be described with standard summary statistics. Continuous variables will be summarized by N, mean, and standard deviation, and categorical variables by the number and percent of subjects in each category. Where appropriate, estimates will be presented with 95% confidence intervals.

Efficacy analyses will attempt to quantify the effects of treatment with NFC-1 relative to placebo. The null hypothesis of no difference between active and placebo will be tested against a 2-tailed alternative with a type-I error rate of 0.05.

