3 OVERALL STUDY DESIGN AND PLAN

This is a randomized, double-blind, placebo-controlled, parallel-group phase 2 study of adolescents to compare the safety and efficacy of NFC-1 with that of placebo. Approximately 90 male and female subjects will receive randomized treatment with NFC-1 or placebo to obtain 80 subjects that complete the study as planned. Subjects must be ≥ 12 to ≤ 17 years of age and have ADHD as defined by the Diagnostic and Statistical Manual of Mental Disorders, 5th edition (DSM-5) and an ADHD-RS-5 ≥ 28 at Baseline. The study will take place in approximately 25 sites in the United States.

The overall maximum study duration for an individual subject is expected to be 70 days with maximum treatment duration of 42 days. As per the schedule of events below (Table 1), subjects will be randomly assigned in a 1:1 ratio to receive either NFC-1 or placebo on Day -1 and will start taking investigational product (IP) at a dose of 100 mg twice daily on Day 1. Dosing will be optimized to 100 mg, 200 mg, or 400 mg twice daily as appropriate, over the 4 weeks of treatment (dose optimization phase), based on clinical response and tolerability. If the subject tolerates their final optimized dose well, the dose will be maintained for an additional 2 weeks (dose maintenance phase) when the primary assessments of efficacy and tolerability will be performed. A follow-up telephone call will be performed 7 days after the last visit.

Table 1. Schedule of Events

		Washand	Wash-out Treatment Period						7-day	
	Screening	Call	Baseline	Dose Optimization				Dose Maintenance		Follow-up Call ^a
Visit	1	No Visit	2	3	4	5	6	7	8/ET	No Visit
Assessment Day	-21	-14	-1	7	14	21	28	35	42	49
Visit Window	± 2 days	± 2 days	± 2 days	± 2 days	± 2 days	± 2 days	± 2 days	± 2 days	± 2 days	+ 5 days
Informed consent/ assent ^b	~									
Psychiatric evaluation (K-SADS-PL)	✓									
WASI-II (brief IQ test)	V									
Inclusion/exclusion criteria	~	✓ (review)	✓ (review)							
Demographics	V									
Randomization			✓							
Medical and medication history ^c	~									
Physical examination	V				3				✓	
Vital signs (resting blood pressure, heart rate, and respiratory rate)	~		~	~	~	~	~	~	~	
Height (calibrated stadiometer)	√				_				~	
Weight (calibrated scale)	V		✓	V	✓	V	✓	✓	✓	
Clinical laboratory test	V		✓	✓	✓	✓	✓	✓	✓	
12-lead ECG	~		✓	~	~	~	✓	~	~	
Serum pregnancy test (females of childbearing potential)	√									

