6.3 Derived and Computed Variables

- Baseline = the last non-missing measurement/assessment before the date of first dose will be flagged. Typically, this will be the value recorded on Day -1.
- Study Day = Assessment Date Date of Randomization + 1
- Change from Baseline = Value at Post-Baseline Value at Baseline
- % Change from Baseline = 100 * Change from Baseline / Value at Baseline
- "Screen Failure" is a patient who has not met eligibility criteria, or otherwise chose not to participate in the study prior to randomization
- ADHD-RS-5 subscales if at least 80% of the questions needed to calculate a scale or subscale score have valid responses, then that score will be computed as the sum of all non-missing items divided by the percentage of items in that scale or subscale present. If fewer than 80% of items have valid responses, then that score will be assigned as missing.
- ADHD-RS-5 Inattention subscale is computed by summing the first 9 item scores for Question 4 Question 12.
- ADHD-RS-5 Hyperactivity-Impulsivity subscale is computed by summing the second 9 item scores for Question 19 Question 27.
- ADHD-RS-5 Total Score is based on 18 items designed to reflect the symptomatology of ADHD based on the DSM-5 criteria. Each item is scored on a 0 (reflecting no symptoms) to 3 (reflecting severe symptoms) and then added for a total score ranging from 0-54.
- ASHS Physiological factor is the mean of Questions 6, 13, 15, 21, and 22.
- ASHS Behavioral Arousal Factor is the mean of Questions 14, 16, and 31.
- ASHS Cognitive/Emotional Factor is the mean of Questions 12, 17, 18, 19, 20, and 32.
- ASHS Sleep Environment Factor is the mean of Questions 23, 24, 25, 26, and 27.
- ASHS Sleep Stability Factor is the mean of Questions 33, 37, and 39.
- ASHS Daytime Sleep Factor is the mean of Questions 4, and 7.
- ASHS Substances Factor is the mean of Questions 9, and 10.
- ASHS Bedtime Routine Factor is the value for Question 30.
- ASHS Total Score is the mean of all 8 subscales, with a higher score indicating better success on each of the dimensions of sleep hygiene.

SAP FINAL Version 2.0

• SCARED Panic Disorder is the summation of Questions 1, 6, 9, 12, 15, 18, 19, 22, 24, 27, 30, 34, and 38.

- SCARED Generalized Anxiety is the summation of Questions 5, 7, 14, 21, 23, 28, 33, 35, and 37.
- SCARED Separation Anxiety is the summation of Questions 4, 8, 13, 16, 20, 25, 29, and 31
- SCARED Social Anxiety is the summation of Questions 3, 10, 26, 32, 39, 40 and 41.

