8 EFFICACY ANALYSIS

8.1 Primary Analysis

The primary efficacy endpoint will be the change in ADHD-RS-5 total score from Baseline to the end of treatment (e.g., Visit 8). For any subjects who discontinue the study prior to Visit 8, their last treated value of the ADHD-RS-5 will be used. That is, the LOCF method of imputation will be employed. The analysis will be performed on the ITT population using an analysis of covariance (ANCOVA) model. The model will use a residual (restricted) maximum likelihood (REML) estimation method and a standard variance components (VC) covariance structure, with treatment group (NFC-1 or placebo) as a fixed factor and baseline ADHD-RS-5 total score as a covariate. The null hypothesis is that there are no differences between the means of the two treatment groups. The hypothesis will be tested at a two-tailed alpha of 0.05. This analysis will be repeated for each of the scheduled visits for ADHD-RS-5 and summarized within the table. Descriptive summaries for actual and change from baseline values will be displayed along with the LS means, LS mean treatment difference, and 95% CIs of the treatment difference, and p-values by visit.

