8.2 Secondary Analysis

Secondary analysis endpoints will include the following measurements (ASHS and SCARED treated as continuous measures):

- Improvement in CGI-I/CGI-S
- Change from baseline in ASHS total score
- Change from baseline in SCARED total score

When appropriate, the analysis for these endpoints will employ the same model and approach as in the primary analysis using an ANCOVA as specified above. Additionally, any subscales for the above primary/secondary endpoints will be included on their corresponding table for the total score (i.e. ADHD-RS-5 Inattention subscale, SCARED Generalized Anxiety, etc.). Please see Section 6.3 for a complete list of derived subscales and composite scores.

Results of the CGI-I assessment will be dichotomized and presented by count and frequency for each week of treatment. CGI-I scores of 1 (very much improved) or 2 (much improved)will be combined into a single category labeled 'Improved', and all other scores (3 [minimally improved] to 7 [very much worse]) will be combined into a single category labeled 'Not Improved'. The

SAP FINAL Version 2.0

observed frequencies of 'Improved' subjects will be compared using a chi-square analysis to test the hypothesis of no association between Improvement and Treatment at type I error rate of 5%.

Page 17 of 88

The CGI-S assessment will be presented similarly. CGI-S scores of 1 (Normal, not at all ill) or 2 (Borderline mentally ill) will be combined into a single category labeled 'Normal or Borderline mentally ill', and all other scores (3 [Mildly Ill] to 7 [Among the most extremely ill patients]) will be combined into a single category labeled 'Mentally ill'.

As to measure treatment response and remission of subjects, three criteria will be defined for each [4]. For response, the criteria are (A) a change in ADHD-RS-5 total score from baseline of 30% or more, (B) a CGI-I score of 1 (very much improved) or 2 (much improved) relative to baseline, and (C) a composite requiring both (A) and (B) to be met. For remission, the criteria are (A) ADHD-RS-5 total score of 18 or less at post-baseline visits, (B) a CGI-I score of 1, and (C) a composite of (A) and (B) to be met. The observed frequency and percentage of subjects in each category will be presented and will be compared using a chi-square analysis to test the hypothesis of no association between response/remission and treatment for each category.

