Summary of CGI-S Improvement by Optimized Dose and Randomized Treatment, by Study Visit Intent-To-Treat Population

{Similar shell as Table 14.2.2.3; Source: Listing 16.2.5.2} {Update footnote to replace CGI-I with CGI-S acronym}

{Update footnote for categorization: CGI-S scores of 1 (Normal, not at all ill) or 2 (Borderline mentally ill) are combined into a single category labeled 'Normal or Borderline mentally ill', and all other scores (3 [Mildly Ill] to 7 [Among the most extremely ill patients]) are combined into a single category labeled 'Mentally ill'.

CONFIDENTIAL AD-ST-33.03 16 Mar 2012 Table 14.2.4.1 Analysis of Change from Baseline in ASHS Total Score and Factors, by Study Visit Intent-To-Treat Population

{Similar shell as Table 14.2.1.1; Source: Listing 16.2.5.3.1, 16.2.5.3.2, 16.2.5.3.3, 16.2.5.3.4} {Update footnote to replace ADHD-RS-5 with ASHS acronym}

Table 14.2.4.2
Summary of Change from Baseline in
ASHS Total Score and Factors by Randomized Treatment, by Study Visit
Intent-To-Treat Population

{Similar shell as Table 14.2.1.2; Source: Listing 16.2.5.3.1, 16.2.5.3.2, 16.2.5.3.3, 16.2.5.3.4} {Update footnote to replace ADHD-RS-5 with ASHS acronym}

Table 14.2.5.1
Analysis of Change from Baseline in
SCARED Score and Factors, by Study Visit
Intent-To-Treat Population

{Similar shell as Table 14.2.1.1; Source: Listing 16.2.5.4.1, 16.2.5.4.2, 16.2.5.4.3, 16.2.5.4.4} {Update footnote to replace ADHD-RS-5 with SCARED acronym}

Table 14.2.5.2
Summary of Change from Baseline in
SCARED Score and Factors by Randomized Treatment, by Study Visit
Intent-To-Treat Population

{Similar shell as Table 14.2.1.2; Source: Listing 16.2.5.4.1, 16.2.5.4.2, 16.2.5.4.3, 16.2.5.4.4} {Update footnote to replace ADHD-RS-5 with SCARED acronym}

Protocol: MDGN-NFC1-ADHD-201

Page 1 of x Final

Table 14.2.6.1 Chi-Square Analysis of Response and Remission Criteria, at End of Study Intent-To-Treat Population

Endpoint Definition	NFC-1	Placebo
Statistic	(N=xx)	(N=xx)
Response[1]		
Definition A		
n	XX	XX
Response	xx (xx x%)	xx (xx.x%)
95% CI	xx x% - xx x%	xx x% -xx x%
p-value [3]	0	XXXX
Definition B		
n	XX	XX
Response	xx (xx x%)	xx (xx.x%)
95% CI	$xx x^{0}/_{0} - xx x^{0}/_{0}$	xx x% -xx x%
p-value [3]	0	XXXX
Definition C		
n	XX	XX
Response	xx (xx x%)	xx (xx.x%)
95% CI	$xx x^{0}/_{0} - xx x^{0}/_{0}$	xx x% -xx x%
p-value [3]	0	XXXX

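### Response, remission and CGI-I improvement get no between-arm effect with an interval, and Remission A and C leave out the baseline covariate that the primary model uses

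*SAP*

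**What the plan says.** SAP 8.2 defines three response and three remission criteria.

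- Response A is "a change in ADHD-RS-5 total score from baseline of 30% or more". Response B is a CGI-I score of 1 or 2. Response C needs both.
- Remission A is "ADHD-RS-5 total score of 18 or less at post-baseline visits". Remission B is a CGI-I score of 1. Remission C needs both.

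All six are "compared using a chi-square analysis to test the hypothesis of no association between response/remission and treatment for each category". The weekly CGI-I split into Improved and Not Improved is also tested by chi-square.

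The shell titled "Chi-Square Analysis of Response and Remission Criteria, at End of Study" (SAP Appendix A, Table 14.2.6.1) shows n, the percentage and a 95% CI within each arm, plus a p-value. Table 14.2.2.1 for CGI-I has the same layout. Neither has a row for a risk difference, odds ratio or relative risk. SAP 11.2 marks both tables as topline.

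The primary model in SAP 8.1 enters treatment group "as a fixed factor and baseline ADHD-RS-5 total score as a covariate", and it reports the treatment difference with a 95% CI. Protocol 13.4.3 sets the general aim: "Efficacy analyses will attempt to quantify the effects of treatment with NFC-1 relative to placebo".

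**The concern.** There are two separate gaps.

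The first is the missing contrast, and it affects every binary efficacy endpoint. A p-value beside two arm-level intervals does not say how large the effect is or how well it is known. In a phase 2 trial with about 45 subjects per arm, that is what the reader most needs from a responder table.

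The second is the missing covariate, and it affects Remission A and C. A fixed end score is much easier to reach from a low baseline than from a high one. An analysis that ignores baseline leaves that variation in the comparison. It gives up some power, and any chance baseline difference between the arms carries through to the remission rates.

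**Working it through.** **The plan's own figure.** The only power statement (Protocol 13.2, SAP 5.1) concerns mean change: effect size 0.7, two-sided 0.05, about 90%. By the normal formula, power = Φ(0.7 × √(n/2) − 1.96). This gives Φ(1.17) = 87.9% at 40 per arm and Φ(1.36) = 91.3% at 45 per arm. No rate or power is stated for response or remission, and nothing below rests on this figure.

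**Fall needed to reach 18.** Entry requires "an ADHD-RS-5 ≥ 28 at Baseline", and the items are "then added for a total score ranging from 0-54".

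| Baseline | Points needed | Per cent of baseline |
|---|---|---|
| 28 | 28 − 18 = 10 | 35.7 |
| 36 | 18 | 50.0 |
| 44 | 26 | 59.1 |
| 54 | 36 | 66.7 |

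The required fall differs 3.6-fold in points across the eligible range. With no treatment effect, simulated remission was 27-44% for baselines of 33 or less and 2-11% for 43 or more. Assumptions: baseline mean 38, SD 5 or 7, cut to 28-54; slope 0.5 or 1.0; residual SD 8 or 10; placebo change −11.

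**Power for Remission A.** Assumptions, none of them in the documents: 45 per arm; baseline mean 38, SD 6.5, cut at 28; placebo change −9; effect 0.7 residual SD; 1,500 simulated trials per setting. The adjusted analysis is logistic regression with baseline.

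| Slope of final on baseline | Residual SD | Chi-square | Adjusted | Gain |
|---|---|---|---|---|
| 0.5 | 8 | 54.4% | 56.3% | 1.9 |
| 0.5 | 10 | 65.5% | 66.8% | 1.3 |
| 0.7 | 8 | 52.3% | 56.0% | 3.7 |
| 0.7 | 10 | 61.3% | 64.1% | 2.8 |
| 1.0 | 8 | 49.1% | 55.3% | 6.2 |
| 1.0 | 10 | 55.3% | 61.3% | 6.0 |

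Repeat runs with these inputs gave 6 to 8 points at slope 1.0. With the −11 placebo change and a 7-point effect (2,000 trials per setting), the gain was 0.7 to 2.2 points at slope 0.5 and 3.8 to 8.8 at slope 1.0. Response A, already relative to baseline, gains about 0 to 3 points.

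**Type I error.** With no effect, chi-square rejected in 4.5-5.8% of trials and the adjusted test in 4.6-6.0%, with simulation error of about 1 point.

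**Baseline imbalance.** With baseline mean 38 and SD 6.5 cut to 28-54, the SD is about 5.6. The SE of the between-arm difference is then 5.6 × √(2/45) = 1.18. A 3-point imbalance shifted remission by 3 to 6.6 percentage points. Scaled to one SE (1.18/3 = 0.39), that is 1.2 to 2.6.

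**What the missing row would show.** Take one simulated setting: remission 19.7% on placebo and 42.9% on NFC-1, 45 per arm, simple normal intervals.

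- Placebo: 19.7 ± 1.96 × √(0.197 × 0.803/45) = 8.1% to 31.3%.
- NFC-1: 42.9 ± 1.96 × √(0.429 × 0.571/45) = 28.4% to 57.4%.
- Difference: 23.2 ± 1.96 × √(0.00352 + 0.00544) = 4.6 to 41.8 points.

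The two arm intervals overlap, yet the interval for the difference excludes zero. It also shows that the effect could be about 5 or about 42 points. The planned table shows neither fact.

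**The case against.** The case for leaving the plan alone has several sound parts.

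- Chi-square is valid under randomisation, and the simulated error rates bear this out. A reader might infer that leaving out baseline biases or invalidates the test; it does not.
- The fixed threshold enters only Remission A and C. A reader might extend the baseline argument to all the criteria. However, Response A is already a percentage of baseline, and Response B, Remission B and CGI-I Improved are ratings of change. The documents give no reason to require the covariate for those.
- The power gain depends on the slope of final on baseline score, which the documents do not give. A gain of several points is not established; it may be as small as 1.
- A 3-point imbalance is about 2.5 SE, roughly a 1% chance in either direction, so its effect should not be read as typical. SAP 7.4 tabulates baseline ADHD-RS-5 by arm, so an imbalance would be visible.
- These are secondary endpoints. SAP 8.1 already gives a baseline-adjusted effect with a CI on the same scale, so the plan does quantify the primary effect. Protocol 13.4.3.2 foresees comparing observed CGI-I proportions, and SAP 10 discloses the chi-square for the CGI scales.

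These points limit the concern without removing it. The crude difference and an interval can be worked out from the counts, but the plan names neither the measure nor the method. SAP 6.1 only allows, as an option, CIs for proportions.

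**Conclusion.** The concern holds as a matter of reporting and precision. The missing between-arm effect needs no assumptions: it can be read directly from the two topline shells, and it covers Response A-C, Remission A-C and CGI-I Improved. The missing covariate matters for Remission A and C. The dependence on baseline is arithmetic (10 points from 28, 26 from 44), but its cost rests on assumed inputs: about 1-2 power points at slope 0.5, about 6-8 at slope 1.0, and a shift of roughly 1-3 percentage points from a one-SE imbalance of about 1.2 points. It would be wrong to conclude that the responder results are invalid or that the primary conclusion is at risk.

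**What to change.** 1. Add the risk difference (NFC-1 minus placebo) with 95% CI to Tables 14.2.2.1 and 14.2.6.1 for every binary endpoint, and name the interval method in SAP 8.2. Table 14.2.3.1 (CGI-S) is built on the first of these shells and would take the same row.
2. Analyse Remission A and C, and optionally Response A, by logistic regression with treatment and baseline ADHD-RS-5 total. Prespecify one method: Firth penalised likelihood throughout, with predicted probabilities standardised over the sample to give the adjusted risk difference and its CI. Do not let observed counts decide between Firth and exact methods. Exact logistic regression does not directly yield a standardised risk difference.
3. Keep the raw proportions and the chi-square tests as supportive.

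The cost is SAP wording, one row in each shell and a short program. No new data are needed. The small downside is some dependence on the model where cells are sparse, most likely in Remission C, which is a reason to keep the raw proportions beside the adjusted result. The change should be made before unblinding, so that the effect measure and the adjustment are not chosen afterwards.

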9 SAFETY AND TOLERABILITY ANALYSIS

The analysis of safety assessments in this study will include summaries of the following categories of safety and tolerability data collected for each subject:

- Adverse Events
 - Summary of all Adverse Events
 - treatment-emergent adverse events (TEAEs), and serious adverse events (SAEs)
 - TEAEs leading to early termination
 - TEAEs by severity
 - TEAEs deemed related to the IP
 - TEAEs occurring in more than 5% of subjects
 - Post-treatment AEs
 - Any deaths
- Clinical Laboratory Investigations(chemistry, Hematology, Urinalysis)
- Vital Signs (systolic and diastolic blood pressure, pulse, respiratory rate, height, weight, and BMI)
- Electrocardiograms (ECG)
- C-SSRS Score
- Concomitant Medications
- Post-treatment Medications
- Study Drug Exposure and Treatment Compliance

All tabulations and summaries for these categories will be performed on the Safety population unless otherwise noted.

9.1 Adverse Events

The causal relationship of the AE to the study drug is determined by the investigator as 'not related', 'unlikely/remotely related', 'possibly related', or 'related'. Any AE determined as

SAP FINAL Version 2.0

'possibly related' or 'related' will be considered 'potentially related' to study drug for purposes of analysis of these events.

Page 18 of 88

Missing and partially missing AE start and/or stop dates will be imputed for the purpose of statistical analysis, according to the specifications described in Section 6.2.

Summaries of incidence rates (frequencies and percentages) of individual TEAEs by MedDRA SOC and preferred term will be prepared. Such summaries will be displayed for TEAEs, SAEs, TEAEs leading to early termination, TEAEs by relationship to study drug, TEAEs by severity, TEAEs occurring in more than 5% of subjects, and Post-treatment AEs.

Each patient/subject will be counted only once within each preferred term If a subject experiences more than one TEAE within a preferred term only the TEAE with the strongest relationship or the maximum intensity, as appropriate, will be included in the summaries of relationship and intensity.

Subject listings of all AEs and SAEs, will be presented.

9.1.1 Adverse Events Leading to Early Termination

A summary of incidence rates (frequencies and percentages) of TEAEs leading to early termination of study drug, by treatment group and overall, SOC, and preferred term, will be prepared for the Safety Population.

A listing of TEAEs leading to early termination will also be provided, displaying details of the event(s) captured on the CRF.

9.1.2 Deaths

A summary and data listing of deaths that occurred will be provided, displaying details of the event(s) captured on the CRF.

9.2 Clinical Laboratory Evaluations

Descriptive summaries of actual (absolute) values and changes from baseline will be presented for Chemistry, Hematology, and Urinalysis analytes. These tables will be grouped by treatment group, and by visit. Summaries will be displayed in conventional units.

The number and proportion of subjects with clinical laboratory values below, within, or above normal ranges, at each study visit will be tabulated (shift tables) for each clinical laboratory analyte by treatment group. Normal ranges for lab results will be provided by the Central laboratory used in this study (i.e., Eurofins).

Laboratory values will be displayed in the data listings and those that are outside the normal range will be flagged, along with corresponding normal ranges.

9.3 Vital Signs

Descriptive summaries of actual (absolute) values and changes from baseline will be presented for systolic and diastolic blood pressure, pulse, respiratory rate, and BMI. These tables will be grouped by treatment group, and by visit.

Additionally, the frequency and percentage of subjects with values of Potential Clinical Importance (PCI) will be summarized in shift tables, by treatment group and overall for each study visit. Criteria for assigning PCI to vital signs are as follows:

SAP FINAL Version 2.0

Criteria for PCI Vital Signs and Change in Body Weight						
Measurement	Lower Criterion	Upper Criterion				
Systolic BP	< 90 mmHg	>120 mmHg				
Diastolic BP	< 50 mmHg	>80 mmHg				
Pulse Rate	≤ 50 bpm	≥ 130 bpm				
Respiration Rate	< 10 breaths/minute	>20 breaths/minute				
Body Weight Change	≥ 7% decrease	≥ 7% increase				

Vital signs and weight/height measurements will also be presented in a subject listing.

